9.2 Registration Procedures

Study participants will be registered into REDCap®, a web based clinical research platform by one of the Study Coordinators.

9.3 Monitoring/Auditing

9.3.1 Data and Safety Monitoring Plan

Data and Safety Monitoring will be performed by a licensed physician who is not a study investigator.

The CRFs and any relevant source documents will be sent to the Study Monitor (as above) who will review them after treatment is complete for subjects 1, 10, 20 and 30.

Complications will be assessed by the co-PIs, categorized into major and minor categories and recorded on the CRF. CRFs and appropriate source documents will be made available to this individual for annually (every 12 months) review to ensure completeness of data collection. Any discrepancies will be immediately addressed by the co-PIs. All adverse events will be recorded and then summarized for inclusion in the final manuscript. Relatedness to the study

procedure will be assessed by an appropriately delegated investigator based on licensure.

Data monitoring will be performed by Study Monitor listed above. CRFs and appropriate source documents will be made available to this individual for bi-monthly review to ensure completeness of data collection. Any discrepancies will be immediately addressed by the co-PIs.

Because this is a small study with only 30 subjects, no DSMB will be used for this study. Data and safety monitoring will be conducted by an individual (Study Monitor) who is not an investigator on this study (see above).

9.3.2 Safety Monitoring

The research coordinator will complete the appropriate report form and logs; assist the PI to prepare reports and notify the IRB, FDA, and/or safety monitor of all Unanticipated Problems/SAE's.

The research coordinator and co-principal investigators will confirm that all Adverse effects (AE) are correctly entered into the AE log by the coordinator; be available to answer any questions that the coordinators may have concerning AEs; notify the IRB and FDA of all Unanticipated Problems/SAEs and AEs as appropriate. All assessments of AEs will be made by a licensed medical professional who is an investigator on the research.

The research coordinator will confirm that the AEs are correctly entered into the AE log. The Study Monitor will confirm that the adverse events are consistent with the source documents and are reported to the appropriate regulatory bodies, as required.

9.3.3 Monitoring Activities

A safety monitor who is not a study investigator (see section 9.3.1) will conduct safety monitoring after treatment is complete for subjects 1, 10, 20, and 30. Adverse events will be documented and reported as described above.

The following issues will be addressed quarterly or more frequently as necessary:

- Verify receipt of all documents and supplies needed to conduct study
- Informed consent obtained for each participant
- CRF completion
- Investigational product accountability
- Check and review of the regulatory binder and all essential documents
- Clinical supply inventory
- SAE reporting
- Enrollment issues and targets
- Protocol amendment and their approval by the IRB
- Significant protocol deviations
- Personnel changes

- Updated regulatory documentation
- Any other issue as deemed important to the conduct of the study

9.3.4 Auditing and Inspecting

The investigator will permit study-related monitoring, audits, and inspections by the Research Quality Assurance Office, IRB, the sponsor, and government regulatory bodies, of all study related documents (e.g. source documents, regulatory documents, data collection instruments, study data etc.). The investigator will ensure the capability for inspections of applicable study-related facilities (e.g. pharmacy, diagnostic laboratory, etc.).

9.3.5 Study Closure

Upon study closure a final evaluation of the data will ensure that all forms are present and complete. Data will be maintained in a secure location for the appropriate duration as described in section 9.4.6. At the conclusion of this term, all forms will be shredded and destroyed.

9.4 Data Management

The online REDCap software system provided by UNC's TraCS Institute will be used for data collection and management, which will ensure that data collected are consistent and follow standardized coding. Data will be entered into REDCap by the study coordinator within 5 business days.

9.4.1 Data Quality

The study team will adhere to the Department of Radiology Internal Monitoring and Quality Assurance Standard Operating Procedures to ensure data quality is maintained for this study. The Department of Radiology's Internal Monitoring and Quality Assurance program will verify a random selection of at least 25% of all source documents for accuracy and completeness.

9.4.2 Missing Value Documentation

The study case report form (CRF) is the primary data collection instrument for the study. All data requested on the CRF must be recorded. All missing data must be explained. If a space on the CRF is left blank because the procedure was not done or the question was not asked, write "N/D". If the item is not applicable to the individual case, write "N/A". All entries should be printed legibly in black ink. If any entry error has been made, to correct such an error, draw a single straight line through the incorrect entry and enter the correct data above it. All such changes must be initialed and dated. DO NOT ERASE OR WHITE OUT ERRORS. For clarification of illegible or uncertain entries, print the clarification above the item, then initial and date it.

Every attempt will be made to ensure that there is as little missing data as possible including reminder phone calls and follow-up phone calls, if a subject misses a

visit. If subjects withdraw, the reason for subject withdrawal will be documented in the study database.

9.4.3 Database Documentation

Copies of completed CRFs with subject IDs will be scanned and sent to the lead study coordinator at UNC for verification through the study database. All study data should be entered in REDCap within 5 business days to ensure timely entry.

9.4.4 Software

The online REDCap software system provided by UNC's TraCS Institute will be used for this study.

9.4.5 Documentation

The research coordinator will monitor the study files on a monthly basis to ensure the appropriate regulatory and IRB documentations are on file and up to date. The research coordinator will also be responsible for ensuring proper study documentation in order to verify compliance with Institutional policy, IRB, FDA and GCP guidelines in the following areas: Informed consent, Protocol, Source Documents and Electronic Case Report Forms.

The co-principal investigators and research coordinator will be responsible for maintaining IRB correspondence. IRB approved forms maintained, as part of the study will include the subject consent form and the HIPAA authorization form.

9.4.6 Data archival and data sharing

It is the investigators' responsibility to retain study essential documents during the investigation and for a period of 2 years after the latter of the following two dates: The date on which the investigation is terminated or completed, or the date that the records are no longer required for purposes of supporting a premarket approval application or a notice of completion of a product development protocol. These documents should be retained for a longer period if required by an agreement with the sponsor. In such an instance, it is the responsibility of the sponsor to inform the investigator/institution as to when these documents no longer need to be retained.

Research records and original signed consent forms are to be retained by principal investigator for at least 6 years if the form includes authorization for use of private health information. Investigators may need to retain these documents for a longer period if required by an agreement with a sponsor or per other applicable regulatory requirements. The 6 year minimum retention of authorizations complies with the privacy regulation requirements.

9.5 Adherence to the Protocol

Except for an emergency situation in which proper care for the protection, safety, and well-being of the study patient requires alternative treatment, the study shall be conducted exactly as described in the approved protocol.

9.5.1 Emergency Modifications

UNC investigators may implement a deviation from, or a change of, the protocol to eliminate an immediate hazard(s) to trial subjects without prior UNC's IRB/IEC approval/favorable opinion.

For any such emergency modification implemented, an IRB modification form must be completed by UNC Research Personnel within five (5) business days of making the change.

9.5.2 Protocol Deviations and Violations

According to UNC's IRB, a protocol deviation is any unplanned variance from an IRB approved protocol that:

- Is generally noted or recognized after it occurs
- Has no substantive effect on the risks to research participants
- Has no substantive effect on the scientific integrity of the research plan or the value of the data collected
- Did not result from willful or knowing misconduct on the part of the investigator(s).

An unplanned protocol variance is considered a violation if the variance meets any of the following criteria:

- Has harmed or increased the risk of harm to one or more research participants.
- Has damaged the scientific integrity of the data collected for the study.
- Results from willful or knowing misconduct on the part of the investigator(s).
- Demonstrates serious or continuing noncompliance with federal regulations, State laws, or University policies.

If a deviation or violation occurs please follow the guidelines below:

Protocol Deviations: UNC personnel will record the deviation and report to any sponsor or data and safety monitoring committee in accordance with their policies. Deviations should be summarized and reported to the IRB at the time of continuing review.

Protocol Violations: Violations should be reported by UNC personnel within one (1) week of the investigator becoming aware of the event using the same IRB online mechanism used to report Unanticipated Problems.

Unanticipated Problems:

Any events that meet the criteria for “Unanticipated Problems” as defined by UNC’s IRB must be reported by the study team using the IRB’s web-based reporting system.

9.6 Amendments to the Protocol

Should amendments to the protocol be required, the amendments will be originated and documented by the Principal Investigator at UNC. It should also be noted that when an amendment to the protocol substantially alters the study design or the potential risk to the patient, a revised consent form might be required.

The written amendment, and if required the amended consent form, must be sent to UNC’s IRB for approval prior to implementation.

9.7 Record Retention

Study documentation includes all eCRFs, data correction forms or queries, source documents, Sponsor-Investigator correspondence, monitoring logs/letters, and regulatory documents (e.g., protocol and amendments, IRB correspondence and approval, signed patient consent forms).

Source documents include all recordings of observations or notations of clinical activities and all reports and records necessary for the evaluation and reconstruction of the clinical research study.

Government agency regulations and directives require that all study documentation pertaining to the conduct of a clinical trial must be retained by the study investigator. In the case of a study with a drug seeking regulatory approval and marketing, these documents shall be retained for at least two years after the last approval of marketing application in an International Conference on Harmonization (ICH) region. In all other cases, study documents should be kept on file until three years after the completion and final study report of this investigational study.

9.8 Obligations of Investigators

The Principal Investigator is responsible for the conduct of the clinical trial at the site in accordance with Title 21 of the Code of Federal Regulations and/or the Declaration of Helsinki. The Principal Investigator is responsible for personally overseeing the treatment of all study participants. The Principal Investigator must assure that all study site personnel, including sub-investigators and other study staff members, adhere to the study protocol and all FDA/GCP/NCI regulations and guidelines regarding clinical trials both during and after study completion.

10.0 PLANS FOR PUBLICATION

Study results will be submitted to a peer-reviewed journal for publication. This study will also be listed on Clinicaltrials.gov and study results will be posted in accordance with appropriate regulations and IJCM requirements.

Neither the complete nor any part of the results of the study carried out under this protocol, nor any of the information provided by the sponsor for the purposes of performing the study, will be published or passed on to any third party without the consent of the study sponsor. Any investigator involved with this study will be obligated to provide the sponsor with complete test results and all data derived from the study.

12.0 APPENDICES

12.1 International Prostate Symptom Score (IPSS)

International Prostate Symptom Score (I-PSS)

Patient Name: _____ Date of birth: _____ Date completed _____

In the past month:	Not at All	Less than 1 in 5 Times	Less than Half the Time	About Half the Time	More than Half the Time	Almost Always	Your score
1. Incomplete Emptying How often have you had the sensation of not emptying your bladder?	0	1	2	3	4	5	
2. Frequency How often have you had to urinate less than every two hours?	0	1	2	3	4	5	
3. Intermittency How often have you found you stopped and started again several times when you urinated?	0	1	2	3	4	5	
4. Urgency How often have you found it difficult to postpone urination?	0	1	2	3	4	5	
5. Weak Stream How often have you had a weak urinary stream?	0	1	2	3	4	5	
6. Straining How often have you had to strain to start urination?	0	1	2	3	4	5	
	None	1 Time	2 Times	3 Times	4 Times	5 Times	
7. Nocturia How many times did you typically get up at night to urinate?	0	1	2	3	4	5	
Total I-PSS Score							

Score: 1-7: *Mild*8-19: *Moderate*20-35: *Severe*

Quality of Life Due to Urinary Symptoms	Delighted	Pleased	Mostly Satisfied	Mixed	Mostly Dissatisfied	Unhappy	Terrible
If you were to spend the rest of your life with your urinary condition just the way it is now, how would you feel about that?	0	1	2	3	4	5	6

About the I-PSS

The International Prostate Symptom Score (I-PSS) is based on the answers to seven questions concerning urinary symptoms and one question concerning quality of life. Each question concerning urinary symptoms allows the patient to choose one out of six answers indicating increasing severity of the particular symptom. The answers are assigned points from 0 to 5. The total score can therefore range from 0 to 35 (asymptomatic to very symptomatic).

The questions refer to the following urinary symptoms:

Questions	Symptom
1	Incomplete emptying
2	Frequency
3	Intermittency
4	Urgency
5	Weak Stream
6	Straining
7	Nocturia

Question eight refers to the patient's perceived quality of life.

The first seven questions of the I-PSS are identical to the questions appearing on the American Urological Association (AUA) Symptom Index which currently categorizes symptoms as follows:

Mild (symptom score less than or equal to 7)
Moderate (symptom score range 8-19)
Severe (symptom score range 20-35)

The International Scientific Committee (SCI), under the patronage of the World Health Organization (WHO) and the International Union Against Cancer (UICC), recommends the use of only a single question to assess the quality of life. The answers to this question range from "delighted" to "terrible" or 0 to 6. Although this single question may or may not capture the global impact of benign prostatic hyperplasia (BPH) Symptoms or quality of life, it may serve as a valuable starting point for a doctor-patient conversation.

The SCI has agreed to use the symptom index for BPH, which has been developed by the AUA Measurement Committee, as the official worldwide symptoms assessment tool for patients suffering from prostatism.

The SCI recommends that physicians consider the following components for a basic diagnostic workup: history; physical exam; appropriate labs, such as U/A, creatine, etc.; and DRE or other evaluation to rule out prostate cancer.

12.2 Adverse Event Questionnaires

Prostatic Artery Embolization Study

IRB#

PI:

Subject ID #: _____

Date of Visit: _____

Adverse Event

Have you experienced any of the following symptoms within the last month?

(Check all that apply)

- Nasal congestion
- Light headedness
- Retrograde ejaculation (Dry ejaculation)
- Priapism (Painful erection lasting 4 or more hours)
- Fatigue or weakness
- Headaches
- Hypotension (Low blood pressure)
- Heart fibrillation or Chest pain
- Swelling in hands, feet, or ankles
- Nausea
- Dizziness
- Fainting
- Erectile dysfunction
- Lower sex drive
- Gynecomastia (Male breast tissue)
- Dysuria (Burning with urination)
- Blood in Urine
- Blood in stool
- Blood in sperm
- Sores on penis
- Sores on buttocks

Form Completed By: _____

Signature

Date

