4.1.8 Visit 3 -1 Day Follow-up

Subjects will be seen in clinic or contacted by phone or by teleconference, per the subject's preference, the day following PAE procedure (+3 days). As most

complications of the procedure will be evident within this time, this visit is to evaluate for early AEs. If an AE is suspected based on change in pain scores or functionality, an appropriate work-up will be performed which may include MRI or CT.

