5.4 Expected Risks

A recent meta-analysis of PAE data from 662 patients in nine studies reported only two major complication (0.3% major complication rate) involving bladder ischemia requiring surgery and severe urinary sepsis requiring hospitalization. Among minor complications transient rectal pain and/or dysuria (9.1%), acute urinary retention (7.9%) and transient hematuria (4.4%) were the most common (1).

Detailed risk analysis is below:

	Risk or Side Effect	Source of Risk or Side Effect	Possible	Less Possible	Rare Events
Potential Risks Associated Study Enrollment & Study Procedures	Discomfort	Blood draw for lab test, ultrasound or MRI	X		
	Thrombophlebitis, bruising, bleeding, blood clot, Pre-syncope or Syncope (i.e. Fainting)	Blood draw for lab tests		X	
	Anxiety or Claustrophobia	MRI scan		X	
	Psychological Discomfort	Clinical Trial			X
	Infection	Blood draw for lab tests			X
	Allergic Reaction	MRI contrast			X
	Gadolinium contrast adverse reaction (i.e. Nephrogenic Systemic Fibrosis or severe skin reaction from contrast agent only reported in patients with kidney dysfunction)	MRI Contrast injection			X
	Confidentiality breach from Medical Records	Medical Record Keeping			X
	Groin/Anesthetic Injection/Neurologic Injury/	Pressure during arterial access and	X		
	Discomfort/Pain	after catheter removed at the leg/femoral artery site	X		
Risks of the PAE	Radiation Exposure Injury	PAE procedure			X
	Kidney Dysfunction	Contrast injected during procedure		X	
	Infection	PAE Procedure		X	

Procedure and Post-operative care	Adverse or Allergic Reaction	Intravenous contrast agent or medications administered as part of procedure or follow-up care (ie. MRI contrast)		X	
	Tissue damage to Skin, Muscle, Skin or other structure in legs and groin (Non-target Embolization)	PAE procedure			X
	Minor Bruising or Bleeding	PAE procedure			X
	Bleeding requiring Transfusion or surgery	PAE procedure			X
	Post Embolization Syndrome, including fever, malaise, headache, and myalgia (body aches)	PAE procedure		X	
	Internal bleeding, such as Gastrointestinal bleeding	Medications taken after the procedure (i.e. Ibuprofen)			X
	Infection	Catheter site in the leg/groin			X
	Arterial injury/trauma, laceration, bruising/pseudo aneurysm	Procedure/ Closure device (clip) on the artery			X
	Pulmonary embolism (clot in lung), Thrombophlebitis (clot in artery or vein)	PAE procedure			X

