To address the secondary aim, we will tabulate the proportion of patients AEs pre- and post-PAE, comparing the proportion using McNemar's test. A p-value <0.05 for McNemar's test will be considered evidence that the proportion of AE's differs for medication, compared to PAE. A p-value >0.05 will be considered inconclusive. We will assume that the adverse events that occur following PAE will be attributed to the procedure and not medication.

We will present the percentage of prostate infarcted at 6 months and the incidence of minor complications at 1 month descriptively, and calculate 95% confidence intervals. Post-acquisition segmentation software will be used to measure infarct volume.

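### The Appendix 12.2 adverse-event checklist has no item for acute urinary retention or rectal pain, so any form-based count in the medication-versus-PAE comparison understates PAE events unless affected men tick another item

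*Combined protocol and SAP*

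**What the plan says.** Section 2.2 makes fewer adverse events with PAE than with medication a secondary aim. For this, section 8.3 states: "we will tabulate the proportion of patients AEs pre- and post-PAE, comparing the proportion using McNemar's test". It does not say which record supplies the counts.

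The only adverse-event instrument in the documents is the form in Appendix 12.2. It asks "Have you experienced any of the following symptoms within the last month" and lists 21 symptoms, from nasal congestion to sores on the buttocks. There is no line for anything else.

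On what to expect after PAE, section 5.4 says: "Among minor complications transient rectal pain and/or dysuria (9.1%), acute urinary retention (7.9%) and transient hematuria (4.4%) were the most common". Its risk table adds access-site discomfort or pain (rated possible) and post-embolization syndrome with fever, malaise, headache and myalgia (rated less possible).

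The 4.3 table schedules adverse-event assessment at Visits 3, 4, 5 and 6, and at neither visit up to and including the procedure. Sections 4.1.8 to 4.1.11 make a work-up conditional: "If an AE is suspected based on change in pain scores or functionality". No pain score or functional scale appears in the 4.3 table or the appendices.

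**The concern.** A paired before-and-after comparison needs events on both sides to be looked for in the same way. The form asks directly about the known drug effects but not about two of the leading PAE complications. A man who had retention and nothing else on the list would return a blank form and count as free of adverse events after PAE.

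If form data feed the test, part of any apparent advantage for PAE could come from the questionnaire. The pre-PAE side cannot be repaired later, because a symptom not asked about while the man was on medication cannot be recovered reliably afterwards.

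**Working it through.** **Step 1: form against the protocol's own lists.** The six drug effects named in section 1.2 (retrograde ejaculation, erectile dysfunction, gynecomastia, lightheadedness, nasal congestion, loss of libido) all have a box: 6 of 6. The PAE effects in section 5.4 compare as follows.

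| Section 5.4 effect | Stated frequency | Box on the form? |
|---|---|---|
| Dysuria | within joint 9.1% | yes |
| Rectal pain | within joint 9.1% | no |
| Acute urinary retention | 7.9% | no |
| Hematuria | 4.4% | yes |
| Headache, malaise (post-embolization syndrome) | less possible | headache yes; malaise plausibly under fatigue or weakness |
| Fever, myalgia (post-embolization syndrome) | less possible | no |
| Access-site pain | possible | no |

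**Step 2: men affected.** N = 30 (section 8.2), or 24 after the 20% dropout mentioned there (30 × 0.80).

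- Retention: 30 × 0.079 = 2.37 men; chance of at least one = 1 − 0.921^30 = 0.915. With 24 men: 1.90 and 0.861.
- Rectal pain or dysuria: 30 × 0.091 = 2.73 men. The rectal-pain share is not given, and the dysuria box would catch some of these men.

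**Step 3: understatement of the post-PAE proportion if the form were the sole source.**

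- Lowest: 0 points, if every affected man also ticks a listed symptom.
- All retention missed: 7.9 points (2.4 of 30 men).
- Extreme: 7.9 + 9.1 = 17.0 points (5.1 of 30 men). This needs no overlap between the two categories, the whole 9.1% to be rectal pain, and no affected man to tick any box.

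**Step 4: effect on the test.** The plan gives no power or expected rate for this comparison, so there is no figure to reproduce. Assumptions: exact two-sided McNemar test at 0.05; pre- and post-PAE events independent; the same true proportion p on both sides, from 20% to 50% (not in the documents); N = 24 or 30. With m the missed proportion, the discordant-pair probabilities are b = p(1 − p + m) for an event before PAE only and c = (p − m)(1 − p) for an event recorded after PAE only.

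Example, N = 30 and p = 0.30:

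- m = 0: b = c = 0.30 × 0.70 = 0.21. The chance of a significant result favouring PAE is 1.25%.
- m = 0.079: b = 0.30 × 0.779 = 0.2337 and c = 0.221 × 0.70 = 0.1547. The chance rises to 5.7%.

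Over all the assumed settings, the chance of a significant result falsely favouring PAE is:

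| Missed | Range |
|---|---|
| 0 points | 0.9% to 1.4% |
| 7.9 points | 4.3% to 6.3% |
| 17.0 points (extreme) | 14% to 35% |

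**The case against.** The strongest reply is that the form is not shown to be the source for the test. Section 8.3 names no instrument. Staff evaluate adverse events at Visits 3 to 6 and make contact the day after PAE to ask about complications (section 4.2.1). The definition in 7.1.1 is open, and post-void residual is measured at 3, 6 and 12 months. A retention event can therefore be recorded without a box on the form. This stands, and it makes the size conditional. It does not supply a structured question for the omitted events, and it does not provide a pre-PAE count collected in the same way, since none is scheduled.

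A reader might infer that the medication-versus-PAE comparison as a whole is tilted towards PAE. The documents do not support that. Section 8.3 attributes all adverse events after PAE to the procedure, while section 4.1.4 lets medication run up to the 3-month visit, so drug symptoms in that period count against PAE. Four scheduled assessments after PAE against none before also give more chances to record events on the PAE side. These features do not repair the form, but they leave the net direction open.

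A reader might also count 15 drug items against 6 procedure items. That split is only a label: headache and fatigue can follow PAE too. The omissions do not depend on it.

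Finally, the condition on pain scores governs when a work-up is done, not whether an event is recorded. Nor do the appendices prove that no scale exists, since the scheduled medication questionnaire is not reproduced there either. The mismatch with the 4.3 table is real but separate.

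**Conclusion.** The concern holds in a limited form. The only adverse-event form supplied covers every drug side effect that section 1.2 names but omits acute urinary retention and rectal pain, as well as fever, myalgia and access-site pain. To the extent that form counts enter the McNemar test, the omission biases them towards PAE.

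The understatement runs from zero to about 8 points for retention alone, and higher if rectal pain is also missed; the 17-point figure is an outer bound, not an estimate. The 8-point case assumes that the section 5.4 rate applies here, that the form is the sole source, and that no man with retention ticks another box. The false-positive figures rest further on assumed event rates of 20% to 50% and on independence.

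This affects a secondary aim and is cheap to correct, so it should be changed.

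**What to change.** 1. Add to the Appendix 12.2 form: unable to pass urine or catheter needed; rectal or pelvic pain; fever or body aches; access-site pain or bruising; and an open-ended line for other symptoms.
2. Give the same form at a pre-PAE visit, adding this to the 4.3 table, and at the post-PAE visits.
3. State in 8.3 that the McNemar test uses this form as its like-for-like source, and which pre- and post-PAE administrations are paired.
4. Separately, reconcile the pain and functionality wording in 4.1.8 to 4.1.11 with the 4.3 table, which schedules no such score. The work-up rule itself is for the investigators.

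Cost: a revised form, one added pre-PAE administration, a new entry in the 4.3 table and a few sentences in 8.3. The reported PAE adverse-event rate may rise slightly.

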4.1.9 Visit 4 -1 Week Follow-up

Subjects will be seen in clinic or contacted by phone or by teleconference, per the subject's preference, one week following PAE procedure (+5 days). As most complications of the procedure will be evident within this time, this visit is to evaluate for early AEs. If an AE is suspected based on change in pain scores or functionality, an appropriate work-up will be performed which may include MRI or CT.

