4.1.10 Visit 5 - 3 Month Follow-Up

Subjects will return 90 +/- 14 days after PAE procedure to complete IPSS, and QOL questionnaires; to have Qmax and PVR measured; medication history questionnaires will be completed; and subjects will be evaluated for possible adverse events. It will be recorded if subjects are unable to hold medications at this time due to residual urinary symptoms. If an AE is suspected based on change in pain scores or functionality, an appropriate work-up will be performed.

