4.3 Time and Events Table

	Visit 1 (Screening)	Visit 2 (Procedure)	Visit 3 (1 Day)	Visit 4 (1 week)	Visit 5 (3 month)	Visit 6 (6 Month)	Visit 7 (12 month)
Informed Consent	X						
MRI	X					X	
PAE procedure		X					
IPSS w/QOL	X				X	X	X
Qmax	X				X	X	X
PVR	X				X	X	X
Medication History Questionnaire	X	X			X	X	
AE Assessment			X	X	X	X	

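### If the one-month adverse-event form is used 1 day and 1 week after PAE, its undated ticks mix earlier drug symptoms with new events and can bias the McNemar comparison against PAE

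*Combined protocol and SAP*

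**What the plan says.** Appendix 12.2 holds one adverse-event form. It asks "Have you experienced any of the following symptoms within the last month" and lists 21 symptoms to tick, with no onset date. The list mixes effects that 1.2 ascribes to BPH drugs (nasal congestion, light-headedness, retrograde ejaculation, erectile dysfunction, gynecomastia) with possible procedure effects such as dysuria and blood in urine.

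The "AE Assessment" row of the 4.3 table is marked at Visits 3, 4, 5 and 6, and not at Visits 1 or 2. Visit 3 is timed as "the day following PAE procedure (+3 days", and 4.1.8 states that "this visit is to evaluate for early AEs". Visit 4 is "one week following PAE procedure (+5 days". For Visit 5, "Subjects will return 90 +/- 14 days after PAE procedure to complete IPSS" and other measures.

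Section 4.1.4 requires at least six months of BPH medication before PAE, and stopping by the 3-month visit. Section 8.3 compares the proportions of patients with AEs before and after PAE by McNemar's test and adds: "We will assume that the adverse events that occur following PAE will be attributed to the procedure and not medication". It does not say which visits or windows form each side. Section 2.3.2 lists AE incidence at 3 months. Section 9.3.1 ("Relatedness to the study" procedure) has a delegated investigator judge causality.

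**The concern.** A form that looks back a month, completed within days of the procedure, mainly asks about the time before it. A man who was light-headed on an alpha-blocker two weeks before PAE could truthfully tick that item the day after PAE.

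McNemar's test uses only the discordant men: those with an event on medication but none after PAE, against the reverse. A man whose earlier drug symptom is recorded again after PAE leaves the first group and becomes positive in both periods. That shrinks the only cell that can support the secondary aim in 2.2, fewer adverse events with PAE than with medication. Where no onset was recorded, old and new symptoms cannot reliably be separated afterwards.

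**Working it through.** The plan gives no power or sample size for the AE comparison, so there is no figure of its own to reproduce. The 81.2% in 8.2 concerns the primary IPSS test only and is unaffected.

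**Step 1: look-back days before PAE.** Take one month as 30 days, so pre-PAE days = 30 − (days since PAE), with a minimum of 0.

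| Visit | Days since PAE | Pre-PAE days of 30 |
|---|---|---|
| 3 | 1 to 4 | 29 to 26 |
| 4 | 7 to 12 | 23 to 18 |
| 5 | 76 to 104 | 0 |

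The Visit 5 window opens no earlier than day 76 − 30 = 46.

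**Step 2: effect on McNemar's test if Visits 3 and 4 count as post-PAE.** Inputs:
- n = 30 (section 3.0).
- p = 0.50, the share of men with an event before PAE. This is an assumption; the documents give none.
- a = 0.214, the share with a procedure event: 9.1% + 7.9% + 4.4% from 5.4, assuming no man has more than one, and independent of p.
- q, the share of men positive before PAE who are recorded again as positive after it because of the look-back. Not given, so varied from 0 to 1.

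Expected discordant counts:
- before only: n·p·(1 − a)·(1 − q) = 30 × 0.50 × 0.786 × (1 − q) = 11.79 × (1 − q)
- after only: n·(1 − p)·a = 30 × 0.50 × 0.214 = 3.21

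Recorded post-PAE rate: a + p·(1 − a)·q = 0.214 + 0.393q.

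Chances below come from full multinomial enumeration of the exact two-sided test at 0.05.

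| q | Before only | After only | Post-PAE rate | Chance PAE shown better | Chance medication shown better |
|---|---|---|---|---|---|
| 0 | 11.8 | 3.2 | 21.4% | 53.5% | 0.0% |
| 0.5 | 5.9 | 3.2 | 41.0% | 7.5% | 0.1% |
| 0.75 | 2.9 | 3.2 | 50.9% | 0.5% | 0.9% |
| 0.9 | 1.2 | 3.2 | 56.8% | 0.0% | 3.7% |
| 1 | 0 | 3.2 | 60.7% | 0 | 9.5% |

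The uncorrected chi-square version, which 8.3 does not rule out, gives 62.6%, 12.3%, 1.9%, 0.1% and 0 for PAE better, and 40.2% for medication better at q = 1. With 24 men (the 20% dropout in 8.2), the exact chance of showing PAE better is 41.2% at q = 0 and 5.4% at q = 0.5.

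**Step 3: range.** For p from 40% to 70% and a from 10% to 30%, with n = 30 and the exact test, the chance of showing PAE better runs from 7.7% to 99.9% at q = 0 and from 0.4% to 74.9% at q = 0.5. It is zero throughout at q = 1.

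**Step 4: when the expected direction reverses.** This needs 11.79 × (1 − q) < 3.21, so q > 1 − 3.21/11.79 = 0.73 in the base case.

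**The case against.** Four points carry weight.

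- **Use of the form at Visits 3 and 4 is inferred.** Sections 4.1.8 and 4.1.9 describe contact to look for early complications, possibly by phone, and mention no questionnaire. The inference rests on the AE row in 4.3 and on 12.2 being the only AE instrument supplied.
- **The named time point has no overlap.** Section 2.3.2 lists AE incidence at 3 months. If the Visit 5 form alone supplies the post-PAE side, the mechanism disappears. But that form reaches back only to day 46 at the earliest. It misses the first days, when 4.1.8 and 4.1.9 expect most complications to be evident, and the first weeks, in which 1.2 expects minor ones to resolve. Section 8.3 also reports minor complications at 1 month, for which Visits 3 and 4 are the only scheduled contacts. If the 3-month incidence is cumulative, the overlap returns.
- **Onset is partly handled.** Section 7.2 asks for onset and resolution dates on the CRF, and the 8.3 rule covers events that follow PAE. Read strictly, a symptom from before PAE is not counted. However, section 7 is written for drugs and contrast agents, nothing links it to the 12.2 form or to McNemar's test, and no text says how a tick for an earlier symptom is removed.
- **Attribution.** The 8.3 sentence is an analysis assumption and 9.3.1 concerns safety recording, so they can coexist. What remains is that the analysis makes no use of the relatedness judgement that the trial collects.

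A reader might infer that the plan does count pre-PAE drug symptoms as procedure events, or that the test cannot favour PAE. The documents support neither: the first needs two unwritten steps (the form used early, and those visits pooled as post-PAE), and the second needs complete carry-over.

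**Conclusion.** The point holds conditionally. The look-back arithmetic follows directly from the form and the visit windows, and the form by itself cannot date a symptom. Whether this reaches McNemar's test depends on the instrument at Visits 3 and 4 and on the visits that define post-PAE, and the plan states neither. Where it does, the bias runs against PAE. In the base case, half carry-over cuts the exact-test chance of showing PAE better from 53.5% to 7.5%. These figures illustrate: the 50% rate, the independence and q are assumptions.

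A reversed result is a further step that a reader might take. In the base case the expected direction reverses only when about 73% or more of the men positive before PAE are re-recorded. Even at full carry-over, the exact test favours medication only 9.5% of the time; the usual result is inconclusive.

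Two linked gaps belong with this point. No AE assessment is scheduled before PAE and 7.2 starts recording at study treatment, so the medication side of the test has no stated data source. And because medication may continue up to the 3-month visit, drug symptoms arising after PAE would be assigned to the procedure even with perfect onset dates. The no-carry-over figures are therefore upper cases.

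**What to change.** - **Visits 3 and 4:** state the instrument. If it is the 12.2 form, ask about the time *since your procedure*, and add to each ticked item an onset field (before or after PAE) and a new-or-worse box.
- **Before PAE:** give the same form, with its one-month look-back, at Visit 1 or 2 and mark it in 4.3. This must accompany the rewording: otherwise the early look-back, the only scheduled capture of on-medication symptoms, is removed and nothing replaces it.
- **Section 8.3, windows:** state which visits and windows feed each side of McNemar's test, and count as post-PAE only events with onset or worsening after PAE.
- **Section 8.3, attribution:** replace the blanket sentence with the investigator's relatedness assessment from 9.3.1, and record whether BPH medication was still being taken at onset.

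The cost is a slightly longer form, one extra form at an existing visit, and a few sentences in 8.3. No visit is added.
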